5 STUDY PROCEDURES

5.A Screening/Baseline Evaluations

Unless otherwise specified, the following evaluations must be performed within 28 days prior to C1, D1:

5.A.1 Medical history, including documentation of all prior lymphoma treatments and documentation of the rationale for treatment of the patient's lymphoma with Zevalin

- 5.A.2 Physical examination, including vital signs (BP, temperature & pulse), height, weight, Body Surface Area (BSA) & performance status (Appendix B).
- 5.A.3 Disease Assessment
 - Total of all measurable indicator lesions
 - CT or PET scan of the chest, abdomen and pelvis is recommended for baseline response evaluation.
- 5.A.4 Laboratory tests including:
 - Complete blood count (CBC) with differential and platelet count
 - Serum chemistries BUN, creatinine, total bilirubin, alkaline phosphatase, LDH, SGOT (AST), SGPT (ALT)
 - Serum beta-2-microglobulin
 - Pregnancy test (serum) for women of childbearing potential
 - Hepatitis B screen (encouraged by Good Medical Practice, but not required)
- 5.A.5 Unilateral or Bi-lateral bone marrow biopsy and aspirate for histology and determination of percent bone marrow involvement
- 5.A.6 Bone marrow cytogenetics (Results are not required prior to enrollment). This can also be done with the repeat Bone Marrow biopsy and aspirate at Cycle 2, Day 29. This does not have to be done at each Bone Marrow biopsy and aspirate, but does need to be completed at either, Baseline or Cycle 2, Day 29.
- 5.A.7 Pathology Review: All patients registered on this study are encouraged to undergo pathology review. The purpose of this review is to verify the histologic diagnosis of an indolent non-Hodgkin lymphoma and that the patients are CD20 positive. Any excess tissue will be retained by the Arizona Cancer Center (unless the patient denies consent).
 - a Pathology materials are to be submitted to:

[name].
Department of Pathology
The University of Arizona Cancer Center
[name]
[name]

[contact]

b The following materials would constitute best available material for review:

- Representative H&E stained slides form the diagnostic biopsy. (Note: Needle aspirates are not adequate for this submission. Consult [name] if adequacy of the specimen is in question.)
- One representative paraffin block which will be conserved (no more than eight additional slides will be cut).
- One copy of the pathology report.

5.B Evaluations During ESHAP Treatment Period

For the purpose of toxicity assessment, the treatment period will include the time from the first ESHAP infusion to 30 days following Zevalin infusion. Evaluations during the 2 cycles of ESHAP are outlined in Appendix A.

5.B.1 ESHAP Cycle 1, Day 1

a. Begin ESHAP Treatment (Please refer to Section 7A for ESHAP administration)

5.B.2 ESHAP Cycle 2, Day 1

- a. History & Physical examination, including vital signs (BP, temperature & pulse), height, weight, Body Surface Area (BSA), and performance status (Appendix B).
- b. Laboratory tests including:
 - Complete blood count (CBC) with differential and platelet count
 - Serum chemistries BUN, creatinine
- c. Toxicity Assessment: Adverse events are to be recorded on an ongoing basis and on appropriate source documents at the clinical site and in the patient's case report form.

5.B.3 ESHAP Cycle 2, Day 29

- a. History & Physical examination, including vital signs (BP, temperature & pulse), height, weight, Body Surface Area (BSA) & performance status (Appendix B).
- b. Laboratory tests including:
 - Complete blood count (CBC) with differential and platelet count
 - Serum chemistries BUN, creatinine
- c. Unilateral or Bi-lateral bone marrow biopsy and aspirate for histology and determination of percent bone marrow involvement
- d. Bone marrow cytogenetics. Does not have to be done at each Bone Marrow biopsy and aspirate, but does need to be completed at either, Baseline or Cycle 2, Day 29.
- e. Disease Assessment:
 - Total of all measurable indicator lesions.
 - CT or PET scan of the chest, abdomen and pelvis
- f. Toxicity Assessment: Adverse events are to be recorded on an ongoing basis and on appropriate source documents at the clinical site and in the patient's case report form.

5.C Evaluations During the Zevalin Imaging & Treatment Period

Ibritumomab Tiuxetan Indium (111 In Zevalin) regimen is administered 4 – 6 weeks after completion of ESHAP.

5.C.1 Day 1

- a. History & Physical examination, including vital signs (BP, temperature & pulse), height, weight, Body Surface Area (BSA), and performance status are to be performed within 28 days of Rituximab & Zevalin administration. (Appendix B).
- b. Toxicity Assessment: Adverse events are to be recorded on an ongoing basis and on appropriate source documents at the clinical site and in the patient's case report form.
- c. Laboratory tests including:
 - Complete blood count (CBC) with differential and platelet count
 - Serum chemistries BUN, creatinine

The above mentioned tests and assessment are to be performed within 28 days of Rituximab & Zevalin administration.

d. Rituxaimab Infusion (250 mg/m²) & ¹¹¹In Zevalin (Ibritumomab Tiuxetan Indium) infusion. (Please refer to section 7.B for detailed treatment administration)

5.C.2 Days 2, 3, 4 and 5

a. Gamma Scan: A scan is to be performed at 48-72 hours after ¹¹¹In Zevalin (Ibritumomab Tiuxetan Indium) infusion. Another optional scan may be performed at 90-120 hours after ¹¹¹In Zevalin (Ibritumomab Tiuxetan Indium) infusion.

CAUTION WILL BE TAKEN IN THE HANDLING OF ALL RADIOACTIVE SAMPLES ACCORDING TO STANDARD PROCEDURES AND PRACTICES AT THE CLINICAL SITE

The purpose of ¹¹¹In Zevalin (Ibritumomab Tiuxetan Indium) imaging is twofold:

- To evaluate biodistribution of whole body gamma camera images
- To assess whether biodistribution is acceptable to proceed with ⁹⁰Y Zevalin (Ibritumomab Tiuxetan Ytrium-90) radioimmunotherapy.

The biodistribution of ¹¹¹In Zevalin (Ibritumomab Tiuxetan Indium) should be assessed by a visual evaluation of whole body planar view anterior and posterior gamma images. A set of images at 48-72 hours after injection is required. To resolve ambiguities, optional images at other time points may be necessary. Images should be acquired using a large field of view gamma camera quipped with a medium energy collimator. Whole body anterior/posterior planar images should be acquired using a large field-of-view gamma camera and medium energy collimators. Suggested gamma camera settings: 256 x 1024 matrix; dual energy photopeaks set at 172 and 247 keV; 15% symmetric window; scan speed of 10 cm/min for the 48-72 hour scan, and 7-10 cm/min for subsequent scans.

> Expected biodistribution:

- Activity in the blood pool areas (heart, abdomen, neck, and extremities) may be faintly visible.
- Moderately high to high uptake in normal liver and spleen.
- Moderately low or very low uptake in normal kidneys, urinary bladder, and normal (uninvolved) bowel.
- Non-fixed areas within the bowel lumen that change position with time; delayed imaging as described above may be necessary to confirm gastrointestinal clearance.

Tumor uptake may be visualized in soft tissue as areas of increased intensity, and tumor-bearing areas in normal organs may be seen as areas of increased or decreased intensity. Tumor visualization on the ¹¹¹In Zevalin (Ibritumomab Tiuxetan Indium) scan is not required for ⁹⁰Y Zevalin (Ibritumomab Tiuxetan Ytrium-90) therapy.

➤ Altered biodistribution

- Intense localization of radiotracer in the liver and spleen and bone marrow indicative of reticuloendothelial system uptake
- Increased uptake in normal organs (not involved by tumor) such as:
 - o Diffuse uptake in normal lung more intense than the liver.
 - o Kidneys with greater intensity than the liver on the posterior view.
 - o Fixed areas (unchanged with time) of uptake in the normal bowel greater than uptake in the liver.
 - o In less than 0.5% of patients receiving ¹¹¹In Zevalin (Ibritumomab Tiuxetan Indium), prominent bone marrow uptake was observed, characterized by clear visualization of the long bones and ribs.

If a visual inspection of the gamma images reveals an altered biodistribution, the patient should not proceed to the ⁹⁰Y Zevalin (Ibritumomab Tiuxetan Ytrium-90) dose. The safety and efficacy of the administration of ⁹⁰Y Zevalin (Ibritumomab Tiuxetan Ytrium-90)in patients with prominent marrow uptake is not known. Possible causes of prominent bone marrow uptake, such as bone marrow involvement by lymphoma, increased marrow activity due to recent hematopoietic growth factor administration, and increased reticuloendothelial uptake in patients with HAMA and HACA, should be considered. Re-assessment of biodistribution after correction of underlying factors should be performed. ⁹⁰Y Zevalin (Ibritumomab Tiuxetan Ytrium-90) should not be administered to patients with persistently prominent marrow uptake on the repeat biodistribution scans.

5.C.3 Day 7, 8 or 9

a. Rituximab Infusion & ⁹⁰Y Zevalin (Ibritumomab Tiuxetan Ytrium-90) Infusion (Please refer to section 7.B for detailed treatment administration)

5.C.4 Day 35 (+/- 7 days)

a. Laboratory tests including:

Complete blood count (CBC) with differential and platelet count. To be done every week until any count abnormalities have passed nadir.

5.D Restaging

5.D.1 3 Months Post-90Y Zevalin (Ibritumomab Tiuxetan Ytrium-90) Infusion

The following tests/evaluations will be obtained 3 months (+/- 7 days) post ⁹⁰Y Zevalin Infusion:

- a. History & Physical examination, including vital signs (BP, temperature & pulse), height, weight, Body Surface Area (BSA) & performance status (Appendix B).
- b. Laboratory tests including:
 - Complete blood count (CBC) with differential and platelet count
 - Serum chemistries BUN, creatinine
 - LDH
- c. Disease Assessment:
 - Total of all measurable indicator lesions.
 - CT or PET scan of the chest, abdomen and pelvis
- d. Toxicity Assessment: Adverse events are to be recorded on an ongoing basis and on appropriate source documents at the clinical site and in the patient's case report form.

5.E Follow-Up Evaluations

5.E.1 Short-Term Follow-Up Period

- a. The following tests/evaluations will be obtained at 6-month intervals (+/- 7 days) for a period of 2 years (24 months) following the Zevalin:
 - History & Physical examination, including vital signs (BP, temperature & pulse), height, weight, Body Surface Area (BSA), and performance status (Appendix B).
 - Laboratory tests including:
 - o Complete blood count (CBC) with differential and platelet count
 - o Serum chemistries BUN, creatinine
 - o LDH
 - Disease Assessment (Only required at 6-month intervals for a period of 2 years (24 months) following Zevalin):
 - o Total of all measurable indicator lesions.
 - CT or PET scan of the chest, abdomen and pelvis (Restaging of disease by CT scan is recommended every 6 months up to Month 24, then annually until year 5).

5.E.2 Long-Term Follow-Up Period

- a. The following tests/evaluations will be obtained annually (+/- 30 days) for an additional 3 years after the completion of the Short-Term Follow-Up period:
 - History & Physical examination, including vital signs (BP, temperature & pulse), height, weight, Body Surface Area (BSA), and performance status (Appendix B).
 - Laboratory tests including:
 - o Complete blood count (CBC) with differential and platelet count
 - o Serum chemistries BUN, creatinine
 - LDH
 - Disease Assessment:
 - o Total of all measurable indicator lesions.
 - o CT or PET scan of the chest, abdomen and pelvis

Once the patients have completed the Short-Term Follow-Up period they will continue to be followed for 3 years on an annual basis (+/- 30 days) for survival and disease status. Patients should be followed by physical exam and, if clinically indicated by Good Medical Practice, CT or PET scans. Patients will be followed for 3 years or until patient starts alternate treatment or is removed from study to allow determination of study endpoints.

5.F Disease Progression Evaluations/Off-Study

Patients who develop disease progression during the treatment period and who do not begin other anti-cancer therapy will continue to be followed for routine safety and efficacy for a total of 30 days following any discontinuation of treatment for any cause.

5.F.1 Tests to be Performed When a Patient is Determined to Have Disease Progression or is Removed from the Study for any Reason

The following tests will be performed within 4 weeks after a patient has demonstrated progression of disease, or removed from study:

It is strictly mandated that patients not be given other myelosuppressive anti-neoplastic agents until recovery from hematologic nadir.

These tests do not have to be repeated if they were performed within 7 days prior to documentation of disease progression.

- a. History & Physical examination, including vital signs (BP, temperature & pulse), height, weight, Body Surface Area (BSA), and performance status (Appendix B).
- b. Laboratory tests including:
 - Complete blood count (CBC) with differential and platelet count
 - Serum chemistries BUN, creatinine

• LDH

c.Disease Assessment (if patient is removed from the study for a cause other than progressive disease):

- Total of all measurable indicator lesions.
- CT or PET scan of the chest, abdomen and pelvis

d.Toxicity Assessment: Adverse Events (AE) are to be recorded on an ongoing basis until resolved or determined to be permanent. All AEs are to be documented on appropriate source documents at the clinical site and in the patient's case report form.

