- 4.A.12 Patients must have absolute neutrophil count (segmented neutrophils and bands) 1,500 /μL and platelets > 100,000/μL within 28 days prior to Cycle 1, Day 1 unless decreased counts have been shown to be due to marrow involvement with NHL.

NOTE: For progression to treatment with Zevalin: Patients must have < 25% bone marrow involvement with lymphoma as determined after cycle 2 of ESHAP. For patients without bone marrow involvement, there must be adequate bone marrow reserves as defined under EXCLUSION. (These criteria must be strictly met for adequate patient safety.)

Additionally, patients must have:

- serum creatinine value < 2.0 and total bilirubin < 2.0.
- Platelet counts $\geq 150,000/\text{mm}^3$, these patients will receive a dose of 0.4 mCi/kg of Zevalin
- Platelet counts from 100,000/mm³ to 149,000/mm³, these patients will receive a 0.3 mCi/kg dose of Zevalin
- 4.A.13 Patients with renal insufficiency or renal failure (serum creatinine > 2.0 mg/dL; creatinine clearance < 50 ml/min) are not eligible for this study. A serum creatinine or creatinine clearance must be obtained within 28 days prior to Cycle 1, Day 1.
- 4.A.14 Pregnant or nursing women may not participate. Women or men of reproductive potential must agree to use an effective contraceptive method as determined by the treating physician from the time of Cycle 1, Day 1 to 6 months after receiving the Zevalin.
- 4.A.15 No prior malignancy is allowed except for adequately treated basal cell or squamous cell skin cancer, in situ cervical cancer, or other cancer for which the patient has been disease-free for 5 years.
- 4.A.16 If Day 28 falls on a weekend or holiday, the limit may be extended to the next working day. In calculating days of tests and measurements, the day a test or measurement is done is considered Day 0. Therefore, if a test is done on a Monday, the Monday 4 weeks later would be considered Day 28. This allows for efficient patient scheduling without exceeding the guidelines.
- 4.A.17 All patients must be informed of the investigational nature of this study and give written informed consent in accordance with institutional and federal guidelines.
- 4.A.18 Expected survival \geq 3 months

4.B Exclusion Criteria

- 4.B.1 Patients with impaired bone marrow reserve, as indicated by one or more of the following:
 - Platelet count < 100,000 cells/mm³
 - Hypocellular bone marrow (cellularity < 10%)

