APPENDIX A

STUDY CALENDAR

4/1/2010

STUDY CALENDAR Page 1

					Ibritumomab Tiuxetan (Zevalin)			
Required Studies	Baseline	ESH	AP Treatm	ent		Regin	nen [∞]	
Visits (weeks or days)	Within28 days prior to C1, D1	Cycle 1 Day 1	Cycle 2 Day1	Cycle 2 Day 29	Day 1	Day 2,3,4,5	Day 7, 8, or 9	Day 35
PHYSICAL								
History / Physical / vital signs ^α	X		X	X	ΧП			
Height / Weight / BSA / PS	X		X	X	ΧП			
Disease Assessment	X			X				
Toxicity Assessment	X		X	X	ΧП			
LABORATORY								
CBC / differential / platelets	X		X	X	ΧП			\mathbf{X}^{Σ}
Serum Creatinine / BUN	X		X	X	ΧП			
AST/ ALT/ Alk. Phos/ T. Bilirubin^	X							
LDH	X							
BHCG [†]	X							
Beta 2- microglobulin	X							
Hepatitis B screen*	X							
Pathology Review [£]	X							
Bone marrow cytogenetics [¥]	X			X				
Bone marrow aspiration and Bx	X			X				
SCANS								
CT or PET Chest	X			X				
CT or PET Abdomen	X			X				
CT or PET Pelvis	X			X				
Gamma Scan						X≠		
TREATMENT								
ESHAP		X	X					
Rituximab 250 mg/m2					X		X	
Ibritumomab Tiuxetan Indium (¹¹¹ In Zevalin)					X			
Ibritumomab Tiuxetan Ytrium-90 (90Y Zevalin)							X	

- α Vital Signs consist of BP, temperature and pulse
- t Baseline for women of childbearing potential
- ¥ A scan is performed at 48-72 hours after 111In Zevalin. Another optional scan may be performed at 90-120 hours after 111In Zevalin.
- ∞ ¹¹¹In Zevalin is administered 4-6 weeks after completion of ESHAP.
- ٨ Required at Baseline and Encouraged to repeat as clinically indicated by Good Medical Practice.
- Encouraged by Good Medical Practice, but not required.
- ¥ Bone Marrow cytogenetics can be done at either Baseline or C2,D29, but must be done at least once.
- £ Pathology Review consists of a basic review of a pathology report. If possible submit: Representative H&E stained slides from the diagnostic biopsy, one representative paraffin block and one copy of the pathology report.
- Σ Starting Day 35 (+/- 7 days) a CBC w/ Diff and Platelet count should be done every week until nadir.
- Within 28 days prior to Rituximab & Zevalin administration..

STUDY CALENDAR Page 2

Required Studies	Restaging	Short-Term Follow-Up				Long-Term Follow-Up	Off-Study [#]
Visits (weeks or days)	3 mos post ⁹⁰ Y Zevalin	6 mos post Zevalin	12 mos post Zevalin	18 mos post Zevalin	24 mos post Zevalin	Follow-Up: Annually for 3 years [£]	Disease Progression or Removed from Study (within 4 weeks)
PHYSICAL							
History / physical / vital signs ^α	X	X	X	X	X	X	X

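### No repeat pregnancy test is scheduled before the Zevalin regimen, so the only result is at least 59 days old at 111In and at least 65 days old at 90Y

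*Combined protocol and SAP*

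**What the plan says.** **Testing.** Section 5.A.4 lists a "Pregnancy test (serum) for women of childbearing potential". The rule that governs that section is that "the following evaluations must be performed within 28 days prior to C1, D1". In Appendix A the BHCG row is marked in the baseline column alone, and its footnote reads "Baseline for women of childbearing potential". The laboratory lists for Cycle 2 Day 1 (5.B.2), Cycle 2 Day 29 (5.B.3) and Zevalin Day 1 (5.C.1) name CBC, BUN and creatinine, with no pregnancy test.

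**Freshness of other results.** For history, examination, toxicity and those laboratory tests, 5.C.1 says: "The above mentioned tests and assessment are to be performed within 28 days of Rituximab & Zevalin administration".

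**Progression to Zevalin.** The note in 4.A.12 sets conditions on marrow involvement and reserve, creatinine, bilirubin and platelets. Pregnancy is not among them. Section 13.B requires a second registration before Zevalin, to reconfirm eligibility and dose, and names no individual criterion.

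**Pregnancy and contraception.** Section 4.A.14 says "Pregnant or nursing women may not participate" and requires contraception "from the time of Cycle 1, Day 1 to 6 months after receiving the Zevalin". Section 7.B.3.c separately recommends contraception during therapy and for up to 12 months afterwards, and condom use for 7 days after 90Y.

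**The concern.** The bar on pregnancy has to hold at two separate treatment steps: the ESHAP cycles, and the radiolabelled antibody given weeks later. Only the first has a test behind it. The protocol treats baseline blood counts and renal function as too old to rely on by Zevalin Day 1, yet relies on the baseline pregnancy result throughout.

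The contraception requirement does not close this gap. It begins at Cycle 1 Day 1, while the test may be up to 28 days earlier. A conception in that interval needs no contraceptive failure, and neither the test nor the contraception requirement covers it. A conception after Cycle 1 Day 1 would need contraception to fail or not to be used. In either case the pregnancy would have to be recognised from history, symptoms or examination. Nausea and vomiting are listed effects of the ESHAP drugs (Section 6.A), so early symptoms could be put down to chemotherapy; that last step is inference.

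At stake is fetal exposure to 111In and then to a therapeutic dose of 90Y. No efficacy estimate is affected.

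**Working it through.** The plan states no age for the pregnancy result, so there is no figure to reproduce. The check is date arithmetic.

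**Inputs**
- Baseline test 0 to 28 days before C1 D1 (5.A). The day of a test counts as Day 0 (4.A.16), so age is a simple difference of dates.
- ESHAP cycle of 28 days, dosing on Days 1 to 4, two cycles (7.A, Table 7).
- Zevalin Day 1 (rituximab and 111In) 4 to 6 weeks, or 28 to 42 days, after completion of the second cycle (7.B).
- 90Y on Day 7, 8 or 9 (7.B), which is 6 to 8 days after 111In.

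**Formula**, with C1 D1 as day 0
- Age at 111In = days from test to C1 D1 + day of completion + 28 to 42
- Age at 90Y = age at 111In + 6 to 8

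The protocol does not say whether completion means the last dose or the end of the 28-day cycle. Both are shown.
- Last dose, C2 D4: 28 + 3 = day 31
- End of cycle 2, C2 D28: 28 + 27 = day 55

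**Results without any delay**

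| Case | Completion = C2 D4 | Completion = end of cycle 2 |
|---|---|---|
| Test on C1 D1, 4 weeks: age at 111In | 0 + 31 + 28 = 59 | 0 + 55 + 28 = 83 |
| Same, 90Y on Day 7: age at 90Y | 59 + 6 = 65 | 83 + 6 = 89 |
| Test 28 days before C1 D1, 6 weeks: age at 111In | 28 + 31 + 42 = 101 | 28 + 55 + 42 = 125 |
| Same, 90Y on Day 9: age at 90Y | 101 + 8 = 109 | 125 + 8 = 133 |

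The first column gives the minima, 59 and 65 days. The lower two rows are illustrations, not maxima, for three reasons:
- A cycle 2 delay of 7 or 14 days (7.A, 8.A.1) adds the same number of days to every entry. With 14 days the minima become 59 + 14 = 73 and 65 + 14 = 79.
- Section 4.A.16 can lengthen the baseline window: "If Day 28 falls on a weekend or holiday, the limit may be extended to the next working day".
- A toxicity delay under 8.B.3 falls between the two rituximab infusions, so it can lengthen the 90Y figure only.

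**With a repeat test** no more than 7 days before 111In, the result is at most 7 days old at 111In and at most 7 + 6 = 13 to 7 + 8 = 15 days old at 90Y. With the 28-day window that 5.C.1 uses, counted from Zevalin Day 1, the limits would be 28 days and 28 + 8 = 36 days.

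**Can the Cycle 2 Day 29 draw carry the test?** C2 D29 is day 28 + 28 = 56.
- Completion at C2 D4: Zevalin Day 1 is day 59 to 73, so the visit is 3 to 17 days earlier.
- Completion at end of cycle 2: Zevalin Day 1 is day 83 to 97, so the visit is 27 to 41 days earlier.

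The draw therefore fits a 7-day window only on the first reading, and only when Zevalin starts within 7 days of the visit.

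**The case against.** The safeguards are real. Pregnancy is barred, contraception is mandatory from C1 D1 and recommended again in 7.B.3.c, history and examination recur at C2 D1, C2 D29 and within 28 days of Zevalin, and 13.B reconfirms eligibility. Few women are likely to be concerned: three cited Zevalin reports give median ages of 60, 54 and 58, the last in an aggressive-histology subset. All of this lowers the risk. None of it orders a test.

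The absence from 5.C.1 is also weaker evidence than it first looks. Bilirubin is a 4.A.12 condition for Zevalin but is missing from the 5.C.1 list too, so that list is not a complete set of eligibility checks. This stands. The difference is that bilirubin is at least named in the 4.A.12 note, whereas a pregnancy result appears in none of the places where progression is decided.

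Cycle 2 of ESHAP is likewise given without a retest, and Section 6.A says that cisplatin, cytarabine and etoposide can cause fetal harm. That stands as well; a test placed before Zevalin does not protect the earlier exposure.

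Four stronger readings are tempting, and the documents do not support them:
- A reader might infer that no pregnancy test at all precedes Zevalin. The baseline test does; what is missing is a repeat.
- A reader might infer that "These criteria must be strictly met for adequate patient safety" covers the whole progression list. It closes the marrow conditions; creatinine, bilirubin and platelets follow it as additional items.
- A reader might infer that a pregnant woman could be dosed in full compliance. Dosing her would breach 4.A.14, even if unknowingly. The accurate statement is that every scheduled test could be done without finding the pregnancy.
- A reader might take the age of the result as a measure of risk. No probability of pregnancy is stated or can be derived.

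**Conclusion.** The point holds as a gap in the safety schedule. The protocol text orders one serum pregnancy test, at baseline, and none before the radiolabelled antibody. The result is at least 59 days old at 111In and at least 65 days old at 90Y. Those minima assume a test on C1 D1 itself, no delay, a 4-week interval counted from C2 D4, and 90Y on Day 7; no other permitted schedule gives a younger result at either dose.

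The number of patients exposed to the gap is probably small but cannot be given, because the share of women of childbearing potential is not stated. The conclusion is confined to the protocol text: the consent pages were not available, and sites may test as routine practice. The documents do not show whether any patient still awaits Zevalin; if none does, the change has no practical effect in this trial. Sample size, error rates and the primary analysis are not involved. The change is worth making because the potential harm is serious and the remedy is cheap.

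**What to change.** For women of childbearing potential:
- Add a serum hCG to the laboratory list in 5.C.1 and to the Zevalin Day 1 column of the Appendix A calendar, in a short stated window before the first rituximab/111In dose. Seven days is an example, not a standard taken from the documents.
- Take it with the pre-Zevalin blood work where the timing allows.
- Add a negative result to the progression note in 4.A.12 and as a named item at the 13.B second registration.

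The cost is one assay per woman concerned and possibly one extra draw, which is needed whenever the C2 D29 visit falls outside the window. The text changes are one line in 5.C.1, one calendar mark, and one item each in 4.A.12 and 13.B. Sample size and analysis do not change.
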